**Hepatic:**

- ALT or AST  $> 5 \times$  ULN
- ALP  $> 2 \times$  ULN (in the absence of known bone pathology)
- Total bilirubin  $> 2 \times$  ULN (in the absence of known Gilbert syndrome)
- Any AST or ALT value  $> 2 \times$  ULN and total bilirubin  $> 1.5 \times$  ULN
- Any ALT or AST value  $> 2 \times$  ULN and INR  $> 1.5$
- Potential Hy's Law cases (defined as ALT or AST  $> 3 \times$  ULN and total bilirubin  $> 2 \times$  ULN [mainly conjugated fraction] without notable increase in ALP to  $> 2 \times$  ULN)
- Any clinical event of jaundice (or equivalent term)
- ALT or AST  $> 2 \times$  ULN accompanied by (general) malaise, fatigue, abdominal pain, nausea, or vomiting, or rash with eosinophilia (eosinophil percent or count above the ULN).

**Cardiac:**

- QTcF at any time  $> 480$  msec
- Bundle branch block (except right bundle branch block that was present prior to MMV367 administration)
- Any arrhythmia, except:
  - sinus bradycardia that is clinically asymptomatic and not associated with any other relevant ECG abnormalities
  - sinus tachycardia that is clinically asymptomatic, is associated with a body temperature  $> 38.0^{\circ}\text{C}$ , and not associated with any other relevant ECG abnormalities
  - respiratory sinus arrhythmia
  - wandering atrial pacemaker, or
  - isolated single premature atrial/ventricular complex (i.e., no bigeminy, trigeminy, couplets, triplets or salvos) that does not occur more than once in a particular ECG tracing.

**Haematological:**

- Haemoglobin drop  $> 20.0$  g/L from baseline (at eligibility visit)
- Absolute neutrophil count (ANC)  $< 0.5 \times 10^9/\text{L}$ .
- Platelet count  $< 75 \times 10^9/\text{L}$ .

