8.3.3 ADVERSE EVENTS OF SPECIAL INTEREST (AESI)

An AE of special interest (AESI), whether serious or non-serious, is one of scientific and medical concern specific to the Sponsor's product or program, for which ongoing monitoring and rapid communication by the Investigator to the Sponsor and medical monitor could be appropriate. Such an event might require further investigation in order to characterise and understand it. Depending on the nature of the event, rapid communication by the trial Sponsor to other parties (e.g., regulators) might also be warranted (CIOMS VI, ICH E2F, 2010). Any abnormalities listed below should be reported as an AESI.

Hepatic:

- ALT or AST $> 5 \times$ ULN
- ALP $> 2 \times$ ULN (in the absence of known bone pathology)
- Total bilirubin $> 2 \times$ ULN (in the absence of known Gilbert syndrome)
- Any AST or ALT value $> 2 \times$ ULN and total bilirubin $> 1.5 \times$ ULN
- Any ALT or AST value $> 2 \times$ ULN and INR > 1.5
- Potential Hy's Law cases (defined as ALT or AST $> 3 \times$ ULN and total bilirubin $> 2 \times$ ULN [mainly conjugated fraction] without notable increase in ALP to $> 2 \times$ ULN)
- Any clinical event of jaundice (or equivalent term)
- ALT or AST $> 2 \times$ ULN accompanied by (general) malaise, fatigue, abdominal pain, nausea, or vomiting, or rash with eosinophilia (eosinophil percent or count above the ULN).

Cardiac:

- QTcF at any time > 480 msec
- Bundle branch block (except right bundle branch block that was present prior to MMV367 administration)
- Any arrhythmia, except:
 - sinus bradycardia that is clinically asymptomatic and not associated with any other relevant ECG abnormalities
 - sinus tachycardia that is clinically asymptomatic, is associated with a body temperature $> 38.0^{\circ}\text{C}$, and not associated with any other relevant ECG abnormalities
 - respiratory sinus arrhythmia
 - wandering atrial pacemaker, or
 - isolated single premature atrial/ventricular complex (i.e., no bigeminy, trigeminy, couplets, triplets or salvos) that does not occur more than once in a particular ECG tracing.

Haematological:

- Haemoglobin drop > 20.0 g/L from baseline (at eligibility visit)
- Absolute neutrophil count (ANC) $< 0.5 \times 10^9/\text{L}$.
- Platelet count $< 75 \times 10^9/\text{L}$.

Dermatological: *†

Clinical signs of possible cutaneous adverse reactions such as:

- Dermatitis
- Rash including
 - erythematous
 - macular
 - papular
 - maculopapular
 - pruritic
 - pustular

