10 SUPPORTING DOCUMENTATION AND OPERATIONAL CONSIDERATIONS

10.1 REGULATORY, ETHICAL, AND STUDY OVERSIGHT CONSIDERATIONS

10.1.1 ETHICAL STANDARD

The trial will be conducted in accordance with the protocol approved by the HREC(s), the principles of the Declaration of Helsinki (Recommendations guiding Medical Doctors in Biomedical Research Involving Human Participants, Fortaleza, Brazil 2013), the NHMRC National Statement on Ethical Conduct in Human Research (2007, updated 2018) and the Integrated Addendum to ICH E6 (R1): Guideline for Good Clinical Practice E6 (R2) (November 2016) — with introductory comments of the Australian TGA.

The Principal Investigator will minimise any discomfort experienced by participants during the trial. The only invasive procedures will be the IV inoculation of the malaria challenge agent and the blood collection by cannulation/venepuncture. The total volume of blood drawn from each participant will not exceed 470 mL in any 30-day period during trial participation.

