12.1.2 ELIGIBILITY CONFIRMATION VISIT (DAY -3 TO DAY -1)

The participants (including reserve participants) will report to the clinical trial unit between Day -3 to Day -1 for the following baseline assessments, unless screening laboratory assessments were conducted within this period, in which case repeat sampling will not be required.

This visit will include:

- Collect blood samples for haematology and biochemistry.
- Perform serum β -hCG pregnancy test for WOCBP.

- Collect urine for urinalysis.
- Collect sample for COVID-19 PCR test.

The timing of these assessments is to ensure that results are available for review by the Investigator prior to inoculation on Day 0.

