##### Safety

- The last scheduled observation prior to the administration of the malaria challenge inoculum [Inoculation Baseline],
- The last scheduled observation prior to the first administration of IMP [Treatment Baseline].

For replicate measurements (e.g., ECG) at baseline, the mean of those replicates will be used as the baseline value.

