#### **11.3.1. Adverse Events**

AEs will be reported according to the volunteer infection studies (VIS) plausible windows and reporting rules:

---

- Inoculum-emergent AEs (IEAEs)= AEs beginning any time from inoculation with the challenge agent until the end of study.
- Treatment-emergent AEs (TEAEs)= AEs beginning any time from administration of the IMP until the end of study.

Adverse Events of Special Interest (AESIs) may be serious or non-serious and are defined by the Sponsor as being of specific scientific and/or medical concern to the Sponsor's product or program. Evaluation on AESI will be based on both Safety Set and FAS depending on if it is treatment emergent or inoculum emergent adverse events.

Any abnormalities listed below should be reported as an AESI.

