#### 11.3.1.2.2. Tables

The number of events, as well as the number and percentage of participants experiencing an AE, will be summarised by, dose group and overall as follows:

Overall summary of IEAEs (FA set)  
Overall summary of TEAEs (IMP set)

Summary of IEAEs by System Organ Class and Preferred Term - All Causalities (FA set)  
Summary of TEAEs by System Organ Class and Preferred Term - All Causalities (IMP set)

Summary of IEAEs by System Organ Class, Preferred Term and Maximum Severity - All Causalities (FA set)

Summary of TEAEs by System Organ Class, Preferred Term and Maximum Severity - All Causalities (IMP set)

Summary of Malaria-Related IEAEs by System Organ Class and Preferred Term (FA set)  
Summary of IMP-Related TEAEs by System Organ Class and Preferred Term (IMP set)

Summary of Malaria-Related IEAEs by System Organ Class, Preferred Term and Maximum Severity (FA set)

Summary of IMP-Related TEAEs by System Organ Class, Preferred Term and Maximum Severity (IMP set)

Summary of IE SAEs by System Organ Class and Preferred Term - All Causalities (FA set)  
Summary of TE SAEs by System Organ Class and Preferred Term - All Causalities (IMP set)

Overall Summary of IE AESIs (FA set)  
Overall Summary of TE AESIs (IMP set)

Summary of IE AESIs by System Organ Class and Preferred Term - All Causalities (FA set)  
Summary of TE AESIs by System Organ Class and Preferred Term - All Causalities (IMP set)

Summary of IEAEs Leading to Study Discontinuation by System Organ Class and Preferred Term - All Causalities (FA set)

Summary of TEAEs Leading to Study Discontinuation by System Organ Class and Preferred Term - All Causalities (IMP set)

For the summary tables, participants who experience the same AE (in terms of the MedDRA preferred term) more than once will only be counted once.

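### A treatment-emergent haemoglobin AESI can include haemoglobin lost before MMV367, and the planned outputs do not split the fall at dosing

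*SAP*

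**What the plan says.** - **Criterion.** SAP 11.3.1 (Haematological) sets a drop of more than 20.0 "g/L from baseline (at eligibility visit"), taken over from Protocol 8.3.3: "Haemoglobin drop > 20.0 g/L from baseline (at eligibility visit"). Protocol 12.1.2 fixes that visit: "ELIGIBILITY CONFIRMATION VISIT (DAY -3 TO DAY -1"). Inoculation is on Day 0 and MMV367 on Day 8.
- **Emergence.** SAP 11.3.1 defines treatment-emergent events as "AEs beginning any time from administration of the IMP until the end of study". Inoculum-emergent events begin at any time from inoculation.
- **Allocation.** SAP 11.3.1 continues: "Evaluation on AESI will be based on both Safety Set and FAS depending on if it is treatment emergent or inoculum emergent adverse events". The sets in SAP section 5 do not include a Safety Set; the table list uses the IMP set.
- **Tables.** SAP 11.3.1.2.2 plans, by dose group and overall, the "Overall Summary of TE AESIs (IMP set") and a breakdown by organ class and preferred term for all causalities.
- **Baselines.** SAP 4.2.2 defines an Inoculation Baseline and a second one: "The last scheduled observation prior to the first administration of IMP [Treatment Baseline"]. For haemoglobin the second is the Day 8 pre-dose sample.
- **Haematology outputs.** SAP 11.3.3 gives change from treatment baseline only, in tables and listings. Protocol 9.4.4 calls for change from each baseline.

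**The concern.** Two separate secondary objectives cover the safety of MMV367 and the safety of the induced infection. The treatment-emergent AESI table by dose group serves the first. Its haemoglobin criterion, however, measures from before the infection, so the count mixes what happened before the drug with what happened after it.

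Haemoglobin is the only AESI in the list defined as a change from a numerical baseline; the other laboratory criteria are limits at a point in time. For one cardiac criterion the SAP does allow for the pre-dose state, by excepting a right bundle branch block present before MMV367. It has no such allowance for haemoglobin.

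Dose groups are small and there is no control arm. In Cohort 1 they hold 3, 2 and 1 participants, so one event is 33%, 50% or 100% of a group. A reader comparing doses would want to know how much of each fall came after dosing.

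**Working it through.** The plan states no expected number of haemoglobin AESIs, so there is no figure to reproduce. The check applies the SAP's rules directly.

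**1. Post-dose fall needed.** Let L be the fall from eligibility to Day 8 pre-dose, and D the further fall after dosing. The criterion is met when L + D > 20. If L is 20 or less, so that the threshold is first passed after dosing, the requirement is D > 20 − L.

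| L (g/L) | D needed (g/L) | Share of the 20 g/L lost before dosing |
|---|---|---|
| 0 | >20 | 0% |
| 5 | >15 | 25% |
| 10 | >10 | 50% |
| 15 | >5 | 75% |
| 19 | >1 | 95% |

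If haemoglobin rose before dosing (L negative), the fall needed is more than 20. No SAP rule sets a minimum for D.

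**2. Three invented participants.**
- 140 g/L at eligibility, 126 pre-dose, 119 post-dose. Fall from eligibility 140 − 119 = 21: a treatment-emergent AESI. Fall from Treatment Baseline 126 − 119 = 7.
- L = 12 and D = 19. Total 31: a treatment-emergent AESI, but not a fall of more than 20 from Treatment Baseline.
- L = 22 and D = 21. The threshold was passed before dosing, so by onset the event is inoculum-emergent only, although the fall after MMV367 exceeds 20.

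The two reference points can therefore disagree in either direction.

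**3. Can the outputs separate L from D?** The data can: haemoglobin is sampled at eligibility, on Day 7 AM and on Day 8 pre-dose. The AESI tables and the planned AESI listing parameters (SAP 11.3.1.1) carry neither fall. The laboratory listings and tables show change from treatment baseline, which is D. The schedule has no haematology sample on Day 0, so the Inoculation Baseline for haemoglobin is the eligibility value. Change from that baseline, which Protocol 9.4.4 would include and SAP 11.3.3 omits, is the quantity that triggers the AESI.

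**4. Is the pre-dose loss negligible?** The documents do not say. Protocol 10.1.1 gives only a ceiling on sampling: "The total volume of blood drawn from each participant will not exceed 470 mL in any 30-day period during trial participation". For scale, take dilution = Hb × (1 − exp(−0.47 / blood volume in litres)), with no regeneration. Assume Hb 130 to 145 g/L, weight 50 to 85 kg and 65 to 75 mL/kg:
- low end: 130 × (1 − exp(−0.47/6.375)) ≈ 9 g/L
- high end: 145 × (1 − exp(−0.47/3.25)) ≈ 20 g/L

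That is the whole 30-day ceiling. Only part of it falls before dosing, and the planned volume is not given.

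**5. Can a ratio be given?** An illustrative simulation drew one normal pre-dose and one normal post-dose fall per participant, each with an assumed SD of 6 g/L.

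| Assumed mean pre-dose fall | Assumed mean post-dose fall | Treatment-emergent by eligibility baseline | Fall >20 from Treatment Baseline | Ratio |
|---|---|---|---|---|
| 0 | 8 | 7.8% | 2.3% | about 3 |
| 0 | 5 | 3.8% | 0.6% | about 6 |
| 10 | 8 | 36.1% | 2.3% | about 16 |
| 10 | 5 | 23.5% | 0.6% | nearly 40 |

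The eligibility baseline gives more events in every row, but the ratio is set almost entirely by the assumed inputs.

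**The case against.** The strongest reply is that treatment-emergent describes timing and makes no causal claim. The tables are for all causalities. Relationship to MMV367, challenge agent, rescue medication and procedures is recorded separately for each event (Protocol 8.3.4.2, SAP 11.3.1.1). A fall judged malaria-related stays out of the IMP-related event tables. **This stands.** A reader might infer that the table overstates haemoglobin AESIs caused by MMV367; the documents do not support that. There is, however, no IMP-related AESI table among those planned.

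A reader might also see a contradiction when an AESI of −21 g/L sits beside a change of −7 g/L in the haematology output. There is none: the figures answer different questions, and both are correct.

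The SAP follows the protocol's criterion. Re-basing it would remove protocol-defined events with post-dose onset, such as the fall of 12 then 19 above, from the treatment-emergent table. That would be anti-conservative and would break reconciliation with the AESI listing. This stands too, so re-basing is not proposed.

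Platelet and neutrophil limits can also be approached before dosing. True, but they are not defined as a change, so they raise no question of which baseline applies.

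Finally, onset of a laboratory AESI is not defined. Taking it as the date the threshold is passed is an inference, supported by Protocol 8.3.1, which says borderline laboratory findings are not routinely adverse events. If a haemoglobin event had been recorded before dosing, the one-record rule in Protocol 8.3.6 would keep its earlier onset and leave it out of the treatment-emergent table.

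**Conclusion.** The concern holds as a gap in presentation. Under the SAP's rules, a treatment-emergent haemoglobin AESI needs a post-dose fall of only 20 g/L minus the pre-dose loss, and the planned AESI outputs do not show how the fall divides at dosing. The arithmetic is exact. Its use rests on one inference, that onset is when the threshold is passed.

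How often this will matter cannot be stated. The documents give no haemoglobin SD, expected fall or planned sampling volume. The direction, more events from the eligibility baseline, holds when haemoglobin on average stays level or falls before dosing. No particular ratio should be quoted.

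The consequence is limited. The trial is descriptive, has at most 18 dosed participants, and states no decision rule that uses this count. A careful reader could rebuild the split from the laboratory listings. It is a cheap improvement that makes the by-dose AESI table readable for the MMV367 safety objective.

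**What to change.** In SAP 11.3.1 and the table list in 11.3.1.2.2:

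1. Keep the eligibility-visit criterion, and keep every reported haemoglobin AESI with post-dose onset in the treatment-emergent AESI tables.
2. Add one derived row to the treatment-emergent AESI table, by dose group: the number of IMP-set participants whose haemoglobin fell more than 20 g/L from Treatment Baseline (Day 8 pre-dose) at any post-dose assessment. Include participants who had already passed 20 g/L before dosing.
3. In the AESI listing, show the fall from eligibility and the fall from Treatment Baseline side by side.
4. Add a footnote saying that the reported count and the derived row use different baselines and can differ in either direction.

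Item 3 also supplies, for these events, the change from the pre-inoculation value that Protocol 9.4.4 leads the reader to expect.

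The cost is one derived flag from haemoglobin values already scheduled, two listing columns and the footnote. Site reporting does not change. The drawback is that the table will carry two haemoglobin counts, and the footnote must explain them.

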**Dermatological: \*†**

---

Clinical signs of possible cutaneous adverse reactions such as:

- Dermatitis
- Rash including
  - erythematous
  - macular
  - papular
  - maculopapular
  - pruritic
  - pustular
  - vesicular

\*If one of these cutaneous reactions is observed, pictures of the lesions should be obtained when feasible.

†Dermatological AEs need not be reported as AESIs if clearly unrelated to the malaria challenge agent or IMP (e.g. rash from cannula dressing or ECG dots).

#### 11.3.1.1. **Parameters**

Parameters to be included in the listings? will be:

- Event Term
- Dates, times and study days of onset and resolution
- Severity (CTCAE Grades 1 to 5)
- Outcome (Not Recovered / Not Resolved; Recovered / Resolved; Recovered / Resolved with Sequelae; Recovering / Resolving; Fatal; Unknown)
- Relationship of AE to IMP (Not Related/Not Suspected, Related/Suspected)
- Relationship of AE to rescue medication (Not Related/Not Suspected, Related/Suspected)
- Relationship of AE to malaria challenge agent (Not Related/Not Suspected, Related/Suspected)
- Relationship of AE to study procedures (Not Related/Not Suspected, Related/Suspected)
- Action taken with IMP (No action taken; Rescue medication administered instead of IMP)
- Other actions taken (including withdrawal from the study)
- Seriousness (and Serious Adverse Event (SAE) criteria)
- AESI status (Yes/No)
- Relatedness to COVID-19 (Yes/No)

Derived parameters:

- Duration in hours
- Time in days of onset relative to first IMP administration

#### 11.3.1.2. **Biostatistical Methods**

All pre-dose AEs occurring before inoculation will be reported as Medical History.

Adverse events (AE) will be coded according to the Medical Dictionary for Regulatory Activities (MedDRA) version 24.1 – Sep 2021 and grouped by system organ class (SOC) and preferred terms (PT). Their severity will be graded according to NCI-CTCAE v5.0 27 Nov 2017.

#### 11.3.1.2.1. **Listings**

All AE data will be listed for each participant, including severity, relationship to IMP, relationship to study procedures, relationship to rescue mediation, relationship to malaria

challenge agent, outcome and actions taken. In addition, listings of AEs leading to discontinuation of the study, SAEs and deaths, will be provided as applicable.

#### 11.3.1.2.2. Tables

The number of events, as well as the number and percentage of participants experiencing an AE, will be summarised by, dose group and overall as follows:

Overall summary of IEAEs (FA set)  
Overall summary of TEAEs (IMP set)

Summary of IEAEs by System Organ Class and Preferred Term - All Causalities (FA set)  
Summary of TEAEs by System Organ Class and Preferred Term - All Causalities (IMP set)

Summary of IEAEs by System Organ Class, Preferred Term and Maximum Severity - All Causalities (FA set)

Summary of TEAEs by System Organ Class, Preferred Term and Maximum Severity - All Causalities (IMP set)

Summary of Malaria-Related IEAEs by System Organ Class and Preferred Term (FA set)  
Summary of IMP-Related TEAEs by System Organ Class and Preferred Term (IMP set)

Summary of Malaria-Related IEAEs by System Organ Class, Preferred Term and Maximum Severity (FA set)

Summary of IMP-Related TEAEs by System Organ Class, Preferred Term and Maximum Severity (IMP set)

Summary of IE SAEs by System Organ Class and Preferred Term - All Causalities (FA set)  
Summary of TE SAEs by System Organ Class and Preferred Term - All Causalities (IMP set)

Overall Summary of IE AESIs (FA set)  
Overall Summary of TE AESIs (IMP set)

Summary of IE AESIs by System Organ Class and Preferred Term - All Causalities (FA set)  
Summary of TE AESIs by System Organ Class and Preferred Term - All Causalities (IMP set)

Summary of IEAEs Leading to Study Discontinuation by System Organ Class and Preferred Term - All Causalities (FA set)

Summary of TEAEs Leading to Study Discontinuation by System Organ Class and Preferred Term - All Causalities (IMP set)

For the summary tables, participants who experience the same AE (in terms of the MedDRA preferred term) more than once will only be counted once.

### ***11.3.2. Concomitant Medication***

Medications used in this study will be coded using WHO Drug Global version B3 Sep 2021 – Added Context.

Concomitant medications are defined as medications continued or newly received at or after administration of the malaria challenge agent through to the End of Study visit.

If a medication has a missing or partial missing start/end date or time and it cannot be determined whether it was taken before initial treatment or concomitantly, it will be considered as prior and concomitant.

Concomitant medications will be summarised by ATC and PN. The summary tables will show the number and percentage of participants taking each medication by ATC and PN.

For the summaries of concomitant medications, participants who take the same medication (in terms of the ATC and PN) more than once will only be counted once for that medication.

Use of rescue medications will be analysed as part of the treatment exposure analysis (Section 9).

### 11.3.3. Laboratory

#### Parameters

##### Haematology

White cell count (WCC)
Neutrophils (NEUT)
Lymphocytes (LYM)
Monocytes (MON)
Eosinophils (EOS)
Basophils (BAS)
Mean cell volume (MCV)
Red cell count (RCC)
Haemoglobin (HGB)
Haematocrit (HCT)
Platelet count (PLAT)
Red cell distribution width (RDW)
Reticulocyte count (RETI)
Blood Group and Rh(D) tests ( Screening only )

##### Biochemistry

Sodium (NA)
Potassium (K)
Chloride (CL)
Bicarbonate (BICARB)
Calcium (CA)
Corrected calcium (CCA)
Magnesium (MAG)
Glucose (GLUC)
Quantitative Glucose 6-Phosphate Dehydrogenase (G6PD) ( Screening only )
Urea
Creatinine (CREAT)
Estimated glomerular filtration rate (eGFR) – CKD Epi calculation
Albumin (ALB)
Globulin
Total protein
Total bilirubin (BILI)
Direct (conjugated) bilirubin (BILDIR)
Alkaline phosphatase (ALP)
Alanine aminotransferase (ALT)
Aspartate aminotransferase (AST)
Gamma-glutamyl transferase (GGT)
Lactate dehydrogenase (LDH)
Phosphate (PHOS)
C-Reactive Protein (CRP) ( not required at Screening )
Cholesterol (Chol) ( Screening only )
Triglycerides (Trig) ( Screening only )
High density lipoprotein (HDL) ( Screening only )
Low density lipoprotein (LDL) ( Screening only )

